10.3 Appendix 3: ECG values and vital signs

10.3.1 Clinically notable laboratory values and vital signs

The following clinically notable laboratory values need to be noted and their clinical significance in light of the underlying PAH condition needs to be considered (does condition cause symptoms; is condition a sign for disease progression; is condition a potential side effect of LTP001 or other PAH directed therapy?)

Clinically Notable Laboratory Values:

Systolic blood pressure > 165 mm Hg or < 80 mm Hg in absence of arterial hyper- or hypotension at baseline

Diastolic blood pressure > 109 mm Hg or < 50 mm Hg in absence of arterial hyper- or hypotension at baseline

Pulse rate > 99 bpm or < 50 bpm and change by 20 bpm or more from baseline

QTcF increase by > 60 ms

All QTcF > 500 ms

QTcF > 480 ms if normal at study entry

QRS-Duration > 120 ms when normal prior to study enrolment.

PR - value > 220 ms when normal at prior to study enrolment

AV-block > Grade 2a

10.4 Appendix 4: Participant Engagement

The following participant engagement initiatives are included in this study and will be provided, as available, for distribution to study participants at the time-points indicated. If compliance is impacted by cultural norms or local laws and regulations, sites may discuss modifications to these requirements with Novartis.

- Thank You letter
- Plain language trial summary - after CSR publication

10.5 Appendix 5: Liver safety monitoring

To ensure participant safety and enhance reliability in determining the hepatotoxic potential of an investigational drug, a standardized process for identification, monitoring and evaluation of liver events has to be followed.

Please refer to [Table 10-1](#) in Appendix 5 for complete definitions of liver laboratory triggers.

Once a participant is exposed to study treatment, every liver event defined in [Table 10-1](#) should be followed up by the Investigator or designated personnel at the trial site, as summarized below. Since deterioration of PAH may result in increases of liver values it should be checked if an increase of liver values might be secondary to a deterioration of right heart failure. Liver chemistry tests (i.e. ALT, AST, TBL, PT/INR, ALP and G-GT) to confirm elevation. Increased liver values considered secondary to deterioration of right heart function are not considered liver events

- Liver chemistry repeats will be performed using the central laboratory. If results will not be available from the central laboratory, then the repeats can also be performed at a local laboratory to monitor the safety of the participant. If a liver event is subsequently reported, any local liver chemistry tests previously conducted that are associated with this event should have results recorded on the appropriate CRF.
- If the initial elevation is confirmed, close observation of the participant will be initiated, including consideration of treatment interruption if deemed appropriate.
- Discontinuation of the investigational drug (refer to the Discontinuation of study treatment [Section 7.1](#)), if appropriate
- Hospitalization of the participant if appropriate
- Causality assessment of the liver event
- Thorough follow-up of the liver event should include, as per the investigator's discretion to allow for a causality assessment: serology tests, imaging and pathology assessments, hepatologist's consultancy; obtaining more detailed history of symptoms and prior or concurrent diseases, history of concomitant drug use, exclusion of underlying liver disease.

All follow-up information and procedures performed must be recorded as appropriate in the eCRF.

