4.1 Overall design

Please refer to [Section 1.2 Schema](#) for study design figure.

This is a non-randomized, open-label extension study over 52 weeks with LTP001 without a control treatment arm. Participants will be presented the opportunity to consider the extension study at the End of Treatment (EOT) visit (Week 25) of the parent study CLTP001A12201. The investigator will assess if the participant will continue by verifying that the participant has completed the parent study as planned. Moreover, at the EOT the investigator will determine the eligibility for the extension study (i.e. that none of the treatment discontinuation criteria were met and that the assessments at the EOT of the parent efficacy study were completed according to the parent protocol). The patient may directly continue into the extension study. If the patient does not directly continue in the extension study, the time between the end of treatment assessments in the parent study and the enrollment in the extension study i.e. during the transition period should be kept to a minimum (it should not exceed 14 days).

Participants who are eligible and want to participate in the extension study will need to have signed an informed consent in order to receive the extension study treatment. In case of a direct transition into the extension study after the end of treatment visit in the parent study, as not all assessment results will be available (e.g. the central lab assessments) at the same day the investigator will re-assess/reconfirm the eligibility as soon as outstanding results are received.

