The safety and efficacy of LTP001 will be checked at the following visits: Weeks 5, 13, 26, 39 and 52, as specified in the Assessment Schedule. Safety and tolerability assessments will take place at each visit. RHC will be performed at week 26, 6MWT and echocardiography will be assessed at Weeks 26 and 52. PAH-SYMPACT and emPHasis-10 will be collected for 7 days intervals with the seventh day of collection occurring within the allotted visit window for all Treatment visits (Weeks 5, 13, 26, 39 and 52). Participants will have safety follow-up phone calls at Weeks 9 and 17, and may be invited for safety assessment at site if deemed necessary. The PI may exercise their discretion in which safety assessments are required at these optional safety follow-up visits. Following the end of treatment period, participants will have one safety follow-up phone call approximately 30 days after the end of treatment visit at Week 52. The duration of the extension study is currently restricted to 52 weeks, but the study may be prolonged (via an amendment to the protocol) if the LTP001 development program in PAH continues and the benefit/risk assessment remains favorable for the patient population studied. The safety and efficacy profile of LTP001 that is observed in this extension study as well as the parent study, CLTP001A12201, will determine continuation of the extension study.

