10.5.1 Liver event and laboratory trigger definitions & follow-up requirements

Table 10-1 Liver event and laboratory trigger definitions

	Definition/ threshold
Liver laboratory triggers If ALT, AST and total bilirubin normal at baseline:	
 • ALT or AST $> 5 \times$ ULN • ALP $> 2 \times$ ULN (in the absence of known bone pathology) • Total bilirubin $> 3 \times$ ULN (in the absence of known Gilbert syndrome) • ALT or AST $> 3 \times$ ULN and INR > 1.5 • Potential Hy's Law cases (defined as ALT or AST $> 3 \times$ ULN and Total bilirubin $> 2 \times$ ULN [mainly conjugated fraction] without notable increase in ALP to $> 2 \times$ ULN) • Any clinical event of jaundice (or equivalent term) • ALT or AST $> 3 \times$ ULN accompanied by (general) malaise, fatigue, abdominal pain, nausea, or vomiting, or rash with eosinophilia • Any adverse event potentially indicative of a liver toxicity
If ALT or AST abnormal at baseline:	
 • ALT or AST $> 3 \times$ baseline or > 300 U/L (whichever occurs first)

Notify Novartis study lead and medical lead of any finding of a liver event identified not explained by PAH worsening for further follow-up assessments.

Table 10-2 Follow up requirements for liver laboratory triggers - ALT, AST, TBL

	ALT	TBL	Liver Symptoms	Action
ALT increase without bilirubin increase:				
	If normal at baseline: ALT $> 3 \times$ ULN	Normal For participants with Gilbert's syndrome: No change in baseline TBL	None	
 • No change to study treatment • Measure ALT, AST, ALP, GGT, TBIL, INR, albumin, CK, and GLDH in 48-72 hours. • Follow-up for symptoms.
	If elevated at baseline: ALT $> 2 \times$ baseline or > 300 U/L (whichever occurs first)			

	ALT	TBL	Liver Symptoms	Action
	If normal at baseline: ALT > 5 x ULN for more than two weeks	Normal For participants with Gilbert's syndrome: No change in baseline TBL	None	
 • Interrupt study treatment • Measure ALT, AST, ALP, GGT, TBIL, INR, albumin, CK, and GLDH in 48-72 hours. • Follow-up for symptoms. • Initiate close monitoring and workup for competing etiologies. • Study treatment can be restarted only if another etiology is identified and liver enzymes return to baseline.
	If elevated at baseline: ALT > 3 x baseline or > 300 U/L (whichever occurs first) for more than two weeks			
	If normal at baseline: ALT > 8 x ULN	Normal	None	
ALT increase with bilirubin increase:				

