Categorical Analysis of QTcF (Fridericia's formula) interval data based on the number of participants meeting or exceeding predefined limits in terms of absolute QT or QTc intervals or changes from baseline will be presented. The number and percentage of participants with clinical notable QTcF will be summarized by visit. A listing of these participants will be provided. The clinical notable criteria for QTcF (Fridericia's formula) are indicated in [Table 2-2](#).

Table 2-2 Clinical notable criteria for QTcF (Fridericia's formula)

ECG parameter (unit)	Clinically notable range
Notable value considering newly occurring or worsening cases	
QTcF (msec)	> 500
QTcF (msec)	> 480 if normal at baseline
QTcF (msec)	> 450
Notable change from baseline	
QTcF (msec)	> 60
QTcF (msec)	> 30

Laboratory data

All laboratory data will be listed by participant and visit/time and if normal ranges are available, abnormalities will be flagged. A separate listing is provided presenting all parameters in a subject with any abnormal values. Descriptive statistics (N, mean, SD, minimum, median, and maximum) summarizing continuous laboratory results of clinical chemistry, hematology, urinalysis, and changes from baseline by visit/time will be provided. Graphical presentations (e.g., boxplots) will be provided by visit/time.

Shift tables using the low/normal/high/ (low and high) classification will be used to compare baseline to the worst on-treatment value.

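### A liver result attributed to right heart deterioration loses liver-event status and lead notification with no stated criteria; separately, no SAP table counts Table 10-1 thresholds or joint ALT/AST and bilirubin rises

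*Protocol*

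**What the plan says.** Appendix 5 of the protocol (Section 10.5) sets up a standard process so that the drug's potential for liver toxicity can be judged reliably. Every event defined in Table 10-1 "should be followed up by the Investigator or designated personnel at the trial site". The same paragraph explains that worsening PAH can itself raise liver values, asks for this to be checked, and then says: "Increased liver values considered secondary to deterioration of right heart function are not considered liver events". It names no criteria, no adjudicator and no size of elevation above which the exemption stops applying.

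Table 10-1 (Section 10.5.1) lists the triggers. One is the potential Hy's Law case: ALT or AST above 3 x ULN with total bilirubin above 2 x ULN, mainly conjugated, and ALP not above 2 x ULN. The table itself carries no PAH exemption. The note below it reads: "Notify Novartis study lead and medical lead of any finding of a liver event identified not explained by PAH worsening for further follow-up assessments".

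For laboratory data, SAP 2.5.1 plans flagged listings, a further listing of all parameters for any participant with an abnormal value, by-visit descriptive statistics including the maximum, boxplots, and one categorical display: "Shift tables using the low/normal/high/ (low and high) classification will be used to compare baseline to the worst on-treatment value". The same section says that no AEs of special interest or AE groupings are defined.

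The setting is Protocol 4.1: "This is a non-randomized, open-label extension study over 52 weeks with LTP001 without a control treatment arm". Long-term safety is the primary objective, and about 40 participants are expected.

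**The concern.** Section 10.5 makes cause part of the case definition. A result can meet a Table 10-1 threshold and still not be a liver event because someone judged that the heart explains it. Yet the same section lists causality assessment as a step to take once an event has been found. The judgement is made open-label, in a disease where hepatic congestion is a credible alternative explanation, and against no written standard.

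The analysis plan would be the natural place to recover such cases without relying on attribution, and it does not do so. No planned table is organised by the thresholds that the protocol itself treats as important, and none looks at transaminases and bilirubin together in the same participant. In an uncontrolled study whose primary aim is safety, a reader of the report should be able to see how many participants crossed those thresholds, whatever the suspected cause.

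**Working it through.** The documents state no figure to reproduce; sample size is marked not applicable in both. The check is a comparison of texts, a trace of reporting routes, and a small illustration.

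**1. The two protocol statements side by side.** Under Section 10.5, a PAH-attributed result is not a liver event. The note under Table 10-1 restricts notification to liver events not explained by PAH worsening. If Section 10.5 governs, that qualifier does no work, because no PAH-explained liver event can exist. If the qualifier does have work to do, a PAH-explained finding is a liver event that is recorded but not notified. Notification to the two leads lapses on both readings. What differs is whether the result is recorded and followed up as a liver event, and whether Section 7.1 applies, since it sends liver events to Appendix 5 for discontinuation guidance.

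For comparison, Section 10.6.1 requires a renal deviation that meets its definitions to be classed as a renal event, with contributing factors documented alongside.

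**2. Routes by which a PAH-attributed potential Hy's Law case reaches the output.**

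| Route | Depends on attribution? | Identifies the joint elevation? |
|---|---|---|
| Liver event (10.5) | Yes | Yes, but no SAP table counts liver events |
| Notification to study and medical leads (10.5.1) | Yes | Not an analysis output |
| Shift tables (SAP 2.5.1) | No | No |
| By-visit maxima and boxplots (SAP 2.5.1) | No | No, one analyte at a time |
| Listings (SAP 2.5.1) | No | Only by reading individual rows |
| AE tables (Protocol 8.6.1, SAP 2.5.1) | Not formally, but the result must be symptomatic, judged clinically significant, or treated | Only through the reported term |
| SAE reporting (Protocol 8.6.3) | No, but the event must be serious | Only through the reported term |

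Two details limit these routes. Section 8.6.1 says that causality for disease progression will usually be recorded as not suspected, so a PAH-attributed AE would usually be absent from the drug-related summary. Section 10.5 asks for earlier local liver tests to go on the CRF if a liver event is later reported; for an exempted result that instruction is not triggered.

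**3. What the shift table can distinguish.** Three hypothetical participants, in multiples of ULN, with anything above 1 coded High:

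| ALT | Bilirubin | ALP | ALT code | Bilirubin code | Meets the numeric Hy's Law trigger? |
|---|---|---|---|---|---|
| 1.2 | 1.1 | 1.0 | High | High | No |
| 3.5 | 2.5 | 1.2 | High | High | Yes |
| 9 | 6 | 1.5 | High | High | Yes |

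All three get the same ALT and bilirubin codes. By-visit maxima do show size, but the largest ALT and the largest bilirubin at a visit may belong to different people. INR is part of another Table 10-1 trigger, and coagulation is not named in the SAP's descriptive laboratory summary.

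**4. Illustrative size.** Take N = 40 from the protocol and assume one case. The exact one-sided 95% upper bound p solves P(X ≤ x | N, p) = 0.05.

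- Not recognised, x = 0: p = 1 − 0.05^(1/40) = 7.2%; observed 0/40 = 0%.
- Recognised, x = 1: (1 − p)^40 + 40p(1 − p)^39 = 0.05 gives p = 11.3%; observed 1/40 = 2.5%.

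If only 30 enrolled (an assumption), the bounds would be 9.5% and 14.9%.

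**The case against.** The strongest reply is that the data survive. Safety samples go to a central laboratory, every abnormal result must be assessed against AE criteria, AE tables are not confined to related events, and SAEs are reported within 24 hours whatever their cause. The DMC is also due to receive extension data (Section 1.1), although Section 10.1.4.1 assures its existence only until the parent study completes. All of this stands.

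A reader might therefore go too far in four ways:

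- **That a potential Hy's Law case drops out of the primary safety summary, or that the SAP tabulates nothing but low/normal/high.** It does not. The values stay in the shift tables, maxima, boxplots and listings, and in the AE or SAE tables where those criteria are met.
- **That the exemption biases the primary result downward.** No liver-event or Hy's Law count is planned, so the exemption changes no planned number. An unexempted case would go uncounted too.
- **That attribution has no cardiac evidence behind it between imaging visits.** Protocol 4.1 does say "RHC will be performed at week 26, 6MWT and echocardiography will be assessed at Weeks 26 and 52". But SAP 2.6.1.1 places NT-proBNP at Days 29, 85 and 267, and physical examination and body weight are scheduled at those visits. What is missing is a rule linking any of these to the attribution.
- **That the investigator alone decides.** This is the natural reading, but Section 10.5 does not say who decides.

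The exemption is also a reasoned choice, since PAH deterioration can raise liver values. That justifies recording the suspected cause. It does not explain the absence of criteria or the conflict with the note under Table 10-1.

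**Conclusion.** Two separate gaps hold. First, the protocol lets an attribution without stated criteria remove liver-event status and lead notification, even from a result meeting the potential Hy's Law trigger, and it contradicts itself on whether a PAH-explained finding is a liver event. Second, the SAP has no table that identifies participants crossing Table 10-1 thresholds or having joint ALT/AST and bilirubin elevation, whatever the cause. The first does not produce the second.

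The consequence is reduced visibility of liver cases within the primary safety objective; the laboratory values themselves are kept. The comparison of 1/40 with 0/40 rests on one assumed case and on a count that the SAP does not currently contain, so it shows scale only. Because the SAP remedy is cheap and serves the primary objective directly, the change should be made.

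**What to change.** **SAP 2.5.1.** Add a table for the whole safety set, derived from laboratory results without regard to investigator attribution, giving the number and percentage of participants who meet each numeric threshold in Table 10-1:

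- peak ALT or AST, total bilirubin and ALP by ULN multiple, with the baseline-relative criteria for those abnormal at baseline;
- ALT or AST above 3 x ULN with INR above 1.5;
- ALT or AST above 3 x ULN with total bilirubin above 2 x ULN and ALP not above 2 x ULN.

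Use scheduled and unscheduled on-treatment results. Show suspected right-heart cause as a separate column, not as an exclusion.

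**Protocol 10.5 and 10.5.1.** The sponsor should reconcile the exemption sentence with the note under Table 10-1, so that it is clear how a threshold-meeting result attributed to PAH is recorded and whether it is notified. The sponsor should also state how the outcome relates to the link in Section 7.1 between liver events and discontinuation guidance. No treatment rule is proposed here.

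**Cost.** One extra table from analytes already collected (Table 8-2), a field for the suspected cause if none exists, and possibly some extra event forms for congestion-related elevations. No additional samples are needed.

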10.5.1 Liver event and laboratory trigger definitions & follow-up requirements

Table 10-1 Liver event and laboratory trigger definitions

	Definition/ threshold
Liver laboratory triggers If ALT, AST and total bilirubin normal at baseline:	
 • ALT or AST $> 5 \times$ ULN • ALP $> 2 \times$ ULN (in the absence of known bone pathology) • Total bilirubin $> 3 \times$ ULN (in the absence of known Gilbert syndrome) • ALT or AST $> 3 \times$ ULN and INR > 1.5 • Potential Hy's Law cases (defined as ALT or AST $> 3 \times$ ULN and Total bilirubin $> 2 \times$ ULN [mainly conjugated fraction] without notable increase in ALP to $> 2 \times$ ULN) • Any clinical event of jaundice (or equivalent term) • ALT or AST $> 3 \times$ ULN accompanied by (general) malaise, fatigue, abdominal pain, nausea, or vomiting, or rash with eosinophilia • Any adverse event potentially indicative of a liver toxicity
If ALT or AST abnormal at baseline:	
 • ALT or AST $> 3 \times$ baseline or > 300 U/L (whichever occurs first)

Notify Novartis study lead and medical lead of any finding of a liver event identified not explained by PAH worsening for further follow-up assessments.

Table 10-2 Follow up requirements for liver laboratory triggers - ALT, AST, TBL

	ALT	TBL	Liver Symptoms	Action
ALT increase without bilirubin increase:				
	If normal at baseline: ALT $> 3 \times$ ULN	Normal For participants with Gilbert's syndrome: No change in baseline TBL	None	
 • No change to study treatment • Measure ALT, AST, ALP, GGT, TBIL, INR, albumin, CK, and GLDH in 48-72 hours. • Follow-up for symptoms.
	If elevated at baseline: ALT $> 2 \times$ baseline or > 300 U/L (whichever occurs first)			

	ALT	TBL	Liver Symptoms	Action
	If normal at baseline: ALT > 5 x ULN for more than two weeks	Normal For participants with Gilbert's syndrome: No change in baseline TBL	None	
 • Interrupt study treatment • Measure ALT, AST, ALP, GGT, TBIL, INR, albumin, CK, and GLDH in 48-72 hours. • Follow-up for symptoms. • Initiate close monitoring and workup for competing etiologies. • Study treatment can be restarted only if another etiology is identified and liver enzymes return to baseline.
	If elevated at baseline: ALT > 3 x baseline or > 300 U/L (whichever occurs first) for more than two weeks			
	If normal at baseline: ALT > 8 x ULN	Normal	None	
ALT increase with bilirubin increase:				
	If normal at baseline: ALT > 3 x ULN	TBL > 2 x ULN (or INR > 1.5) For participants with Gilbert's syndrome: Doubling of direct bilirubin	None	
	If elevated at baseline: ALT > 2 x baseline or > 300 U/L (whichever occurs first)			
	If normal at baseline: ALT > 3 x ULN	Normal or elevated	Severe fatigue, nausea, vomiting, right upper quadrant pain	
	If elevated at baseline: ALT > 2 x baseline or > 300 U/L (whichever occurs first)			

Table 10-3 Follow up requirements for liver laboratory triggers - Isolated Hyperbilirubinemia

Criteria	Actions required	Follow-up monitoring
Total Biliruin (isolated)		
>1.5 – 3.0 ULN	
 Maintain treatment Repeat LFTs within 48-72 hours 	Monitor LFTs weekly until resolution to ≤ Grade 1 or to baseline
> 3 - 10 × ULN (in the absence of known Gilbert syndrome)	
 Interrupt treatment Repeat LFT within 48-72 hours Hospitalize if clinically appropriate Establish causality Record the AE and contributing factors (e.g. conmeds, med hx, lab) in the appropriate CRF 	Monitor LFTs weekly until resolution to ≤ Grade 1 or to baseline (ALT, AST, total bilirubin, Alb, PT/INR, ALP and GGT) Test for hemolysis (e.g. reticulocytes, haptoglobin, unconjugated [indirect] bilirubin)
> 10 x ULN	
 Discontinue the study treatment immediately Hospitalize the participant Establish causality Record the AE and contributing factors (e.g. conmeds, med hx, lab) in the appropriate CRF 	ALT, AST, total bilirubin, Alb, PT/INR, ALP and GGT until resolution (frequency at Investigator discretion)
Any AE potentially indicative of a liver toxicity	
 Consider study treatment interruption or discontinuation Hospitalization if clinically appropriate Establish causality Record the AE and contributing factors (e.g. conmeds, med hx, lab) in the appropriate CRF 	Investigator discretion

Based on Investigator's discretion investigation(s) for contributing factors for the liver event can include: Serology tests, imaging and pathology assessments, hepatologist's consultancy; obtaining more detailed history of symptoms and prior or concurrent diseases, history of concomitant drug use, exclusion of underlying liver disease.

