7.1 Discontinuation of study treatment

The investigator must also contact the IRT to register the participant's discontinuation from study treatment.

Discontinuation of study treatment for a participant occurs when study treatment is permanently stopped for any reason (prior to the planned completion of study drug administration, if any) and can be initiated by either the participant or the investigator.

The investigator must discontinue study treatment for a given participant if he/she believes that continuation would negatively impact the participant's well-being.

Discontinuation from study treatment is required under the following circumstances:

- Participant decision
- Pregnancy (if the participant decided to terminate the pregnancy, treatment with LTP001 may be resumed after the abortion procedure if desired by the participant and agreed by the investigator and the Novartis medical monitor).
- Any situation in which continued study participation might result in a safety risk to the participant
- Development of heart failure symptoms consistent with pulmonary hypertension WHO Functional Class IV (symptoms at rest; severe symptoms at exercise)
- If organ transplantation becomes necessary during the study treatment
- Atrial septostomy required due to deterioration of PAH
- Deterioration of PAH suggesting ineffectiveness of LTP001 as per the judgement of the investigator
- Adverse event that is graded severe or serious by the investigator and considered study drug related. If the investigator believes it is beneficial for the participant to stay on study drug (e. g. signs of PAH-improvement and adverse event appears well manageable) and the participant wishes to stay on study drug the investigator shall contact the Novartis medical monitor for further discussion.
- If a liver or renal event occurs, follow guidelines outlined in [Section 10.5](#) (Appendix 5) and [Section 10.6](#) (Appendix 6) regarding discontinuation of study treatment.

If discontinuation from study treatment occurs due to participant's decision, the investigator should make a reasonable effort to understand the primary reason for the participant's discontinuation from study treatment and record this information. In those instances where study drug discontinuation criteria were waived as per the exceptions defined above the decision made as well as the rationale for it needs to be documented in writing in the Trial Master File.

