9.9 Sample size determination

Not applicable

10 Supporting documentation and operational considerations

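### Protocol Tables 10-1 and 10-2 do not match: some rows that may change study treatment meet no liver-event trigger, and some liver events have no specific action row

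*Protocol*

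**What the plan says.** Protocol Section 10.5 refers the reader to Table 10-1 "for complete definitions of liver laboratory triggers" and states that "every liver event defined in [Table 10-1](#) should be followed up by the Investigator or designated personnel at the trial site". The note under Table 10-1 asks the site to notify the sponsor's study and medical leads of a liver event that PAH worsening does not explain. Section 7.1 sends liver events to Section 10.5 for the decision on stopping treatment.

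Table 10-1 has two baseline headings. The first requires ALT, AST and total bilirubin all to be normal, and lists eight triggers covering ALT or AST, ALP, bilirubin, INR, potential Hy's Law, jaundice, symptoms and liver-related adverse events. The second, "If ALT or AST abnormal at baseline", lists one: ALT or AST above 3 x baseline or above 300 U/L.

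Table 10-2 names ALT, AST and TBL in its title, but every aminotransferase criterion in it is for ALT. Its rows with TBL above 2 x ULN or INR above 1.5, and its symptom row, read "If elevated at baseline: ALT > 2 x baseline or > 300 U/L (whichever occurs first" for participants with an elevated baseline. The multiple of 3 x baseline appears only in the row for elevations lasting more than two weeks. The symptom row lists "Severe fatigue, nausea, vomiting, right upper quadrant pain".

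Table 10-3 covers isolated bilirubin rises and ends with a row for any adverse event that might indicate liver toxicity.

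**The concern.** Long-term safety is the primary objective, and Section 10.5 aims at a standardized process for finding and evaluating liver events. Liver-event status brings the Section 10.5 follow-up steps, the notification under Table 10-1 and the Section 7.1 route to a treatment decision. If the defining table and the action table disagree, a site can be in an action row without a liver event, or have a liver event without a row to apply.

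Abnormal baselines, where most of the conflict lies, are foreseeable. Section 10.5 itself says that deterioration of PAH may raise liver values, and Sections 5.1 and 5.2 set no liver-test limit for entry. The parent study's criteria are not in these documents.

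**Working it through.** The plan states no figure here to reproduce. The check sets the table rules side by side.

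**Abnormal baseline, 2 x against 3 x.** Let B be an elevated baseline ALT in U/L, with AST at or below its own trigger.

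- Table 10-2's bilirubin/INR and symptom rows need ALT > 2B or ALT > 300, that is, ALT > min(2B, 300).
- Table 10-1 needs ALT > 3B or ALT > 300, that is, ALT > min(3B, 300).
- A value in Table 10-2 but not in Table 10-1 therefore lies above min(2B, 300) and up to min(3B, 300). Such values exist only when 2B < 300, so B < 150.

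| Assumed B (U/L) | 2B | min(3B, 300) | Unmatched ALT (U/L) |
|---|---|---|---|
| 60 | 120 | 180 | above 120 to 180 |
| 80 | 160 | 240 | above 160 to 240 |
| 100 | 200 | 300 | above 200 to 300 |
| 120 | 240 | 300 | above 240 to 300 |
| 149 | 298 | 300 | above 298 to 300 |
| 150 | 300 | 300 | none |

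The conflict needs raised bilirubin, raised INR or listed symptoms as well. ALT above 2B alone falls in Table 10-2's first row, which leaves treatment unchanged and asks for a repeat test. That is monitoring below the event threshold, not a contradiction.

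**Constructed profiles.** ULN for ALT and AST is not given, so 35, 40 and 55 U/L were assumed; the results were the same for all three. Unless stated, baseline is normal and other values are unremarkable.

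| Profile | Table 10-1 trigger | Numeric or symptom row in Table 10-2 or 10-3 |
|---|---|---|
| Baseline ALT 1.5 x ULN, now 3.75 x ULN (2.5 x baseline), TBL 2.5 x ULN | none | 10-2, bilirubin/INR row |
| Same ALT, INR 1.8 | none | 10-2, bilirubin/INR row |
| Same ALT, nausea | none | 10-2, symptom row |
| AST only, 6 x ULN | yes | none |
| AST only, 4 x ULN, TBL 2.5 x ULN | yes, potential Hy's Law | none |
| Baseline AST 1.5 x ULN, now 5 x ULN, ALT normal | yes | none |
| ALT 4 x ULN with malaise, mild fatigue, or rash with eosinophilia | yes | none |
| Only TBL raised at baseline (1.4 x ULN), ALT 6 x ULN, TBL 2.5 x ULN | no heading applies | 10-2, bilirubin/INR row |
| ALT 6 x ULN for one week, TBL normal | yes | 10-2, no change to treatment |
| Isolated TBL 4 x ULN | yes | 10-3, interrupt |

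The last two profiles show the tables agreeing.

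**Symptoms.** Right upper quadrant pain falls within Table 10-1's abdominal pain, and severe fatigue within its fatigue, so at normal baseline Table 10-1 is the broader list. A participant with ALT above 3 x ULN and only malaise, non-severe fatigue or rash with eosinophilia has symptoms, and so is outside Table 10-2's rows for no symptoms. The symptom row does not name these symptoms.

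**Bilirubin-only baseline.** Table 10-1's first heading needs normal bilirubin and its second needs abnormal ALT or AST, so raised bilirubin alone meets neither. Table 10-2 nonetheless makes provision for Gilbert's syndrome.

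**The case against.** A reader might infer that these participants escape follow-up, or that sites have no treatment instruction. The documents do not support that. For any Table 10-1 event, including an AST-only one, Section 10.5 asks for confirmation, close observation, consideration of interruption, discontinuation or hospitalization where appropriate, and causality assessment. The last row of Table 10-3 asks the site to consider interruption or discontinuation for a liver-related adverse event. In the 2 x to 3 x band, Table 10-2 itself orders retesting and workup if its blank Action cells continue the cell above. Section 8 asks for immediate safety concerns to be discussed with the sponsor, and Section 8.6.3 requires serious events to be reported within 24 hours.

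These provisions narrow the gap without closing it. The Section 10.5 and Table 10-3 treatment steps are discretionary, and a laboratory value is an adverse event only if it meets the Section 8.6.1 criteria. None of them gives an AST-only event a specific row or makes an ALT-bilirubin pattern in the band a defined liver event.

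A reader might also infer that the primary safety results are biased through an undercount of liver events. No such count is planned. SAP Section 2.5.1 defines no adverse events of special interest; it reports adverse event summaries, laboratory listings and shifts to the worst value, with no use of Table 10-1 thresholds.

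Two layout questions also stand. The jaundice and liver-related adverse event triggers sit under the normal-baseline heading as the text was extracted. If they apply to everyone, some symptomatic cases in the band become liver events, but bilirubin-only or INR-only patterns do not automatically do so. Whether the blank Action cells call for interruption is likewise an inference. The AST, symptom-list and bilirubin-only-baseline mismatches, and the difference between 2 x and 3 x, do not depend on it.

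**Conclusion.** The tables contradict each other in four places: the baseline multiple when bilirubin or INR is raised or symptoms are present, AST, the symptom list, and bilirubin-only abnormality at baseline. In the band above 2B and up to min(3B, 300) U/L, with raised bilirubin or INR, the participant is in the follow-up table but meets no Table 10-1 laboratory trigger. The liver-event follow-up and notification tied to Table 10-1 then do not apply as written. AST-only events, including a potential Hy's Law case met through AST, are left with the discretionary text and the adverse event row of Table 10-3.

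The consequence is inconsistent identification, notification and handling of liver events between sites. The documents give no frequency of abnormal baselines or of these patterns among the approximately 40 expected participants, so the number affected cannot be estimated. Values attributed by the site to right heart deterioration are not liver events under Section 10.5, which reduces that number by an unknown amount.

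**What to change.** The sponsor's clinical team should reconcile Tables 10-1, 10-2 and 10-3, and the matching CRF trigger logic, so that:

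- each Table 10-1 event maps to a stated action row;
- each row that calls for a change to study treatment corresponds to a defined liver event;
- every participant falls under a baseline heading, and it is clear which triggers apply whatever the baseline;
- each row shows its own action, so that nothing depends on reading merged cells.

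Rows that only ask for monitoring may stay below the event threshold. The choice of analytes, multiples, symptoms and actions belongs to the sponsor. The rows that call for interruption must also be reconciled with Section 6.5, which does not permit it; that is a separate point.

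The cost is a protocol amendment with revised table wording, an update to the CRF logic, and possibly a few more notified events. No new assessments are needed.
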